5.2 Exclusion Criteria

1. Pregnant women are excluded from this study because ⁹⁰Y-DOTATOC is a *Class C* agent with potential teratogenic or abortifacient effects.
2. Because there is an unknown but potential risk for adverse events in nursing infants secondary to treatment of the mother with ⁹⁰Y-DOTATOC, breastfeeding should be discontinued until 6 weeks after the last administration of study drug.
3. Surgery within 4 weeks of study drug administration.
4. External beam radiation to both kidneys (scatter doses of <500 cGy to a single kidney or radiation to < 50% of a single kidney is acceptable).

5. Prior PRRT with ⁹⁰Y-DOTATOC (TATE) or ¹⁷⁷Lu-DOTATOC (TATE) or ¹³¹I-MIBG therapy for this malignancy.
6. Another investigational drug within 4 weeks of study drug administration.
7. Concurrent, malignant disease for which patient is on active therapy.
8. Another significant medical, psychiatric, or surgical condition which is currently uncontrolled by treatment and which would likely affect the subject's ability to complete this protocol.
9. Any subject for whom, in the opinion of their physician, a 12-hour discontinuation of somatostatin analogue therapy represents a health risk. Also subjects who have received SandostatinLAR in the past 28 days or long-acting lanreotide within the past 8 weeks are excluded. Subjects may be maintained on short acting octreotide during the time from last injection of long-acting somatostatin analogue until 12 hrs prior to injection of study drug. Known antibodies to Octreotide, Lanreotide, or DOTATOC or history of allergic reactions attributed to compounds of similar chemical or biologic composition to ⁹⁰Y-DOTATOC.
10. Patients who have had chemotherapy within 4 weeks (6 weeks for nitrosoureas or mitomycin C) of study drug administration or those who have not recovered from adverse events due to agents administered more than 4 weeks earlier.
11. Uncontrolled illness including, but not limited to ongoing or active infection, symptomatic congestive heart failure, unstable angina pectoris, cardiac arrhythmia, or psychiatric illness/social situations that would limit compliance with study requirements.
12. Subject weighs more than 450 pounds. (Subjects who weigh more than 450 pounds will not be able to fit inside the imaging machines.)
13. Inability to lie still for the entire imaging time (due to cough, severe arthritis, etc.)

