6.0 Imaging and Treatment Plan

**Phase II,
Dosimetry-Guided, Peptide Receptor Radiotherapy (PRRT) with
⁹⁰Y-DOTA-tyr³-Octreotide (⁹⁰Y-DOTATOC) in Children and Adults
with Neuroendocrine and other Somatostatin Receptor Expressing Tumors**

Treatment Cycles and Followup		Imaging and Treatment Schedule	Initial ⁹⁰ Y-DOTATOC Dose	Cumulative ⁹⁰ Y-DOTATOC Dose	Cumulative Renal Radiation
Cycle 1 Week 1	Day 1	Physical exam with height, weight, vitals, labs, list, GFR, pregnancy test; QOL questionnaire Start 18 hrs IV/PO fluids			
	Day 2	⁹⁰ Y-DOTATOC + IV amino acids Continue IV/PO fluids for 48 hrs	50 mCi/m ² in children; 120 mCi in adults	120 mCi maximum	
	Day 4	⁹⁰ Y-DOTATOC PET/CT			
Cycle 2 Week 7-9	Day 1	Physical exam with height, weight, vitals, labs, med list, GFR, pregnancy test Start 18 hrs IV/PO fluids			
	Day 2	⁹⁰ Y-DOTATOC + IV amino acids Continue IV/PO fluids for 48 hrs	Dosimetry determined	270 mCi maximum	
	Day 4	⁹⁰ Y-DOTATOC PET/CT			
Cycle 3 Week 13-17	Day 1	Physical exam with height, weight, vitals, labs, list, GFR, pregnancy test Start 18 hrs IV/PO fluids			
	Days 2-3	⁹⁰ Y-DOTATOC + IV amino acids Continue IV/PO fluids for 48 hrs	Dosimetry determined	420 mCi maximum	≤ 23 Gy
FU	3 months after treatment 3	Physical exam with height, weight, vitals, labs, med list, GFR; QOL questionnaire, diagnostic CT (MRI)			
	6-9 months after treatment 3	Physical exam with height, weight, vitals, labs, med list, GFR; diagnostic CT (MRI) ⁶⁸ Ga-DOTATOC PET/CT;			

Treatment consists of 3 cycles, 6-8 weeks apart. Cycle 1 dose is fixed. Cycles 2 and 3 doses will be determined by dosimetry-based calculation of renal doses from previous cycles; total renal dose ≤ 23Gy.

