8.0 Duration of Therapy and Stopping Rules

8.1 Stopping Rules for individual subject

In the absence of treatment delays due to adverse events, treatment may continue for 3 cycles or until one of the following criteria applies:

- Cumulative renal radiation dose exceeds 23 Gy.
- Intercurrent illness prevents further administration of treatment.
- Unacceptable adverse event(s) such as irreversible renal or hematopoietic toxicity.
- Initiation of another tumor specific therapy.
- Patient decides to withdraw from the study.
- General or specific changes in the patient's condition render the patient unacceptable for further treatment in the judgment of the investigator.

Other causes of discontinuation from study:

- Termination of study by Sponsor.
- Subject's condition no longer requires study drug.

* Note: Disease progression alone does not mandate discontinuation of ⁹⁰Y treatment.*

Disease progression per RECIST 1.1 criteria during the follow up period will warrant removal from study.

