An unexpected allergic reaction following the administration of ^{90}Y -DOTATOC or the amino acids may consist of shortness of breath, wheezing, lowering of blood pressure, fever, chills, hives, itchiness or damage to the blood vessels. The amino acid solution is hyperosmolar and may cause local inflammation or in rare cases, blistering at the infusion site. A 20 gauge IV line or PICC line is recommended to avoid this inflammation. A phone call will be made to subjects 3-5 days following each infusion of amino acids to assess skin changes at the injection site. The long-term effects of ^{90}Y -DOTATOC are unknown. ^{90}Y -DOTATOC may cause radiation damage that may not surface until months or years later.

Participation in this study may be hazardous to a fetus or a nursing child. There is not enough information to determine whether there are significant risks to a nursing child or a fetus conceived or

carried by a subject who is participating in this study. Therefore, in order to participate, all females capable of becoming pregnant must have a negative pregnancy test within 7 days prior to the first ^{90}Y -DOTA-tyr³-octreotide treatment. Female subjects must tell us if they may have become pregnant within the previous 14 days because the pregnancy test is unreliable during that time. All subjects capable of becoming pregnant must agree to practice a medically acceptable birth control measure (abstinence, birth control pills, intrauterine devices, vaginal diaphragm, vaginal sponge, or condom with spermicidal jelly) throughout the study and for eight months following the end of the last treatment. Any females who are nursing must refrain from nursing while on study and for three months following the end of the last treatment.

9.3 Expected Adverse Events Associated with Amino Acid Infusions:

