10.3 Concomitant Therapy

The subject may not receive any other approved or investigational anti-neoplastic therapies for the treatment of the refractory somatostatin-receptor positive tumor during the course of the study, excluding somatostatin analogues and bisphosphonates. However, all subjects on somatostatin analogue therapy will discontinue therapy from 12 hours prior to a) injection with ^{68}Ga -DOTATOC, and b) infusion with ^{90}Y -DOTA-tyr³-Octreotide until 12 hours post administration. Subjects who have been on hormonal therapy (other than somatostatin analogues) for ≥ 2 months with SD or PD may continue to receive hormonal therapy during this study. Subjects who initiate another tumor-specific therapy will be discontinued from further treatment with ^{90}Y -DOTA-tyr³-Octreotide. Patients may continue long acting Somatostatin analogues between cycles of ^{90}Y therapy. It should be administered as standard of care after completion of dosimetry imaging for Cycles 1 and 2. Following Cycle 3, it may be given on Day 3 or later. Patients on long acting Lanreotide should have this treatment held until after ^{90}Y treatment Cycle 3. Short acting somatostatin analogue can be used at the discretion of the treating physician to bridge the patient.

All subjects who have received at least one dose of ^{90}Y -DOTA-tyr³-Octreotide must continue into the Long-Term Follow-up Study Period at the point of treatment discontinuation. This is necessary to determine any long-term effects of treatment with ^{90}Y -DOTA-tyr³-Octreotide.

Subjects may receive, at the discretion of the investigator, appropriate medical treatment for medical problems that arise while on study.

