Pregnancy status: male // female: premenarchal / >60y.o. / negative serum pregnancy / post menopausal x 12 M / ultrasound negative
- 2 Y / N Breastfeeding women.
- 3 Y / N Surgery within 4 weeks of study drug administration.
- 4 Y / N External beam radiation to both kidneys (scatter doses of <500 cGy to a single kidney or radiation to < 50% of a single kidney is acceptable).
- 5 Y / N Prior PRRT with ⁹⁰Y-DOTATOC (TATE) or ¹⁷⁷Lu-DOTATOC (TATE) or ¹³¹I-MIBG therapy for this malignancy.
- 6 Y / N Another investigational drug within 4 weeks of study drug administration.
- 7 Y / N Concurrent, malignant disease for which patient is on active therapy.
- 8 Y / N Another significant medical, psychiatric, or surgical condition which is currently uncontrolled by treatment and which would likely affect the subject's ability to complete this protocol.
- 9 Y / N Any subject for whom, in the opinion of their physician, a 12-hour discontinuation of somatostatin analogue therapy represents a health risk. Also subjects who have received long-acting somatostatin analogue in the past 28 days or long-acting lanreotide within the past 16 weeks are excluded. Subjects may be maintained on short acting octreotide during the time from last injection of long-acting somatostatin analogue until 12 hrs prior to injection of study drug. Known antibodies to Octreotide, Lanreotide, or DOTATOC or history of allergic reactions attributed to compounds of similar chemical or biologic composition to ⁹⁰Y-DOTATOC.
Last somatostatin therapy: long acting date and type: _____
short acting usage: _____
- 10 Y / N Patients who have had chemotherapy within 4 weeks (6 weeks for nitrosoureas or mitomycin C) of study drug administration or those who have not recovered from adverse events due to agents administered more than 4 weeks earlier.
Date of last chemotherapy: _____
- 11 Y / N Uncontrolled illness including, but not limited to ongoing or active infection, symptomatic congestive heart failure, unstable angina pectoris, cardiac arrhythmia, or psychiatric illness/social situations that would limit compliance with study requirements.
- 12 Y / N Subject weighs more than 450 pounds. (Subjects who weigh more than 450 pounds will not be able to fit inside the imaging machines.)
- 13 Y / N Inability to lie still for the entire imaging time (due to cough, severe arthritis, etc.)

Signature of Investigator: _____

Date: _____

Physical exam for ⁹⁰Y-DOTATOC

Subject Data

1) Limited Physical Exam:

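### Section 5.2 lets nursing resume 6 weeks after the last dose, about 7 weeks sooner than section 9.2 permits

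*Combined protocol and SAP*

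**What the plan says.** Two sections of the protocol set a nursing period.

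- **Section 5.2 (Exclusion Criteria), item 2:** "breastfeeding should be discontinued until 6 weeks after the last administration of study drug". The reason given is an unknown but possible risk to the infant.
- **Section 9.2 (Expected Adverse Events Associated with ⁹⁰Y-DOTATOC):** nursing women "must refrain from nursing while on study and for three months following the end of the last treatment". The same paragraph says that too little is known to judge whether the risk to a nursing child is significant.

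The entry checklist in Appendix III lists "Breastfeeding women" as an exclusion and gives no time at which nursing may resume. Section 9.2 does not define when a subject is on study. The treatment plan in section 6.0 places the last scheduled follow-up visit "6-9 months after treatment 3".

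**The concern.** The two instructions cover the same women, the same drug and the same infant risk, and both count from the last treatment. They differ in length (6 weeks against three months) and in force: section 5.2 advises, section 9.2 requires. Neither refers to the other.

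Section 5.2 is where staff are likely to look when a nursing woman asks about joining. Someone relying on it alone could tell her that she may resume at 6 weeks, when the mandatory rule in section 9.2 still forbids it. Where the protocol itself calls the risk unknown, it should give one answer.

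**Working it through.** The plan states no figure for the gap, so there is none to reproduce. The check is date arithmetic on the two stated periods.

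**Inputs**

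- Section 5.2, item 2: 6 weeks = 6 × 7 = 42 days after the last dose.
- Section 9.2: three months after the last treatment. Over every start date from 2017 to 2020, three calendar months last 89 to 92 days, with a mean of 91.3.
- Section 9.1.3: physical half-life of ⁹⁰Y, 64.1 hours.

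**Gap between the two rules**

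Gap = three calendar months − 42 days.

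- Shortest: 89 − 42 = 47 days = 6.7 weeks.
- Longest: 92 − 42 = 50 days = 7.1 weeks.
- Mean: 91.3 − 42 = 49.3 days = 7.0 weeks.

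The gap is therefore about 7 weeks.

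**Are the rules compatible?** The periods are nested. A woman who follows section 9.2 also satisfies section 5.2, but one who follows only section 5.2 may break section 9.2.

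**Physical decay at 6 weeks**

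- 42 days × 24 = 1,008 hours.
- 1,008 / 64.1 = 15.7 half-lives.
- Fraction left by physical decay alone: 0.5^15.7 ≈ 0.00002, or about 0.002%.

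For comparison, the reporting window in section 9.1.3 is 10 half-lives: 641 hours / 24 = 26.7 days, rounded up to 27. Six weeks is already longer than that.

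**If the on-study clause in section 9.2 ran to the last follow-up visit.** This is conditional on a reading discussed under the objection.

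- Six months (181 to 184 days): gap of 139 to 142 days, about 20 weeks.
- Nine months (273 to 276 days): gap of 231 to 234 days, about 33 weeks.

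**The case against.** The strongest case against acting is that nothing practical follows. The two rules never force incompatible actions, since keeping to section 9.2 satisfies both. Section 5.2 is an eligibility list and not a counselling script, and the checklist used at entry gives no permission to resume. What a woman is told would normally be in the consent form, which was removed from the documents reviewed. By 6 weeks almost no ⁹⁰Y remains by physical decay. Most of this stands, and it keeps the importance low. It does not remove the contradiction: the protocol gives two periods, and even if 6 weeks is judged enough, section 9.2 would then need correcting.

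A reader might infer a much larger gap, of 20 to 33 weeks, by taking the on-study clause to cover all of follow-up. Two places lend this some colour. Section 8.1 says "Disease progression per RECIST 1.1 criteria during the follow up period will warrant removal from study", and section 10.3 says that treated subjects "must continue into the Long-Term Follow-up Study Period at the point of treatment discontinuation". But neither defines the phrase used in section 9.2. On that reading the three-month clause would add nothing for a woman who completes follow-up and would matter only for those who leave early. The contraception rule just before it in section 9.2 has the same form, with a tail of eight months after the last treatment. The more natural reading of both is the treatment period plus a fixed tail. The larger figures are therefore a possibility for the clinical team to rule out, not a finding.

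**Conclusion.** The inconsistency is real. Section 5.2, item 2 ends the nursing restriction about 7 weeks (47 to 50 days) before section 9.2 does, and nothing supplied reconciles the two. The size rests on reading three months as calendar months and on counting both periods from the last dose. For that reason 49 days is a typical value and should not be quoted as a minimum.

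A reader might also infer that the shorter period would harm infants. The documents do not support that: they give no data on transfer into milk, and 6 weeks is already 15.7 physical half-lives. Nor can it be said that any woman has been or would be wrongly advised, because the consent form could not be seen. Only a woman who stopped nursing in order to take part and wishes to resume is affected, which means very few subjects. This is a low-importance correction to a safety instruction, with no bearing on any endpoint, error rate or sample size.

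**What to change.** 1. In section 5.2, item 2, change the period from 6 weeks to three months, still counted from the last dose.
2. In section 9.2, state the same period in the same words: no nursing from the first dose until three months after the last dose.
3. Before making the second edit, have the clinical team confirm that the on-study clause was not meant to extend the restriction through follow-up. If it was, both sections should state that longer period. This is a safety decision and not an editorial one. The undefined phrase should not be copied into section 5.2.
4. Check that the consent form gives the same period.

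The cost is wording in two sections and one check. The downside is a restriction about 7 weeks longer than section 5.2 now gives, for very few women. Endpoints, sample size and analysis do not change.

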9.4 Research radiation dose estimate

9.5 Risks of ^{90}Y -DOTATOC PET/CT Scan Procedure

Risks of Investigational PET/CT: Additional risks include radiation exposure from the investigational low dose CT scan and the inconvenience of the investigational PET/CT scan. Children may require sedation or anesthesia to remain still during the PET/CT scanning procedure. The risks of sedation include a reaction to the medication used for sedation or anesthesia. If anesthesia is required, there is a risk of injury to the throat or airways from insertion of the breathing tube.

10.0 Dosing Delays/Dose Modifications

10.1 Dosage Modifications

Dosimetry will be acquired following treatments 1 & 2. The kidney dose/mCi will be calculated and the total target dose that will limit renal dose to ≤ 23 Gy. The target dose minus 120 mCi will then be divided into two equal doses for Cycles 2 and 3 with adjustments based on dosimetry. Regardless of the total dose to kidneys as determined by dosimetry, the maximum dose in Cycle 2 will be 150 mCi; Cycle 3 will be limited to \leq Cycle 2.

Dose of ^{90}Y -DOTATOC will be decreased 25-50% for any subject in whom dosimetry measurement on first or second dose indicates probable total renal dose for three cycles will be >23 Gy. Dose may be increased on subsequent cycles so long as summation of dosimetry measurements limits total renal dose to ≤ 23 Gy.

Dose of ^{90}Y -DOTATOC will be increased 10-20% for any subject in whom dosimetry measurement on first or second dose indicates probable total renal dose for three cycles will be significantly <23 Gy. No subject will receive > 420 mCi total dose of ^{90}Y -DOTATOC.

Subjects who had a nuclear GFR measured at baseline will be followed for nephrotoxicity by nuclear GFR. If they demonstrate a $\geq 30\%$ decrease in GFR as determined by nuclear GFR scan, their dose will be reduced by 50% on the next cycle. Full dose may then be given when GFR returns to 90% of baseline. Patients who experience $\geq 30\%$ decrease in GFR will be placed on an age appropriate dose of captopril or other ACE inhibitor.

Also, patients that experience a rise in serum creatinine above 1.2 (who previously had normal levels) will be hydrated and have their serum creatinine repeated. If the creatinine level after hydration remains

elevated above 1.2, then nuclear GFR will be measured. If applicable, dose reductions will be implemented as described above.

Nephrotoxicity as demonstrated by $\geq 50\%$ decrease in nuclear scan GFR will be considered a DLT if the resulting GFR is below normal for subject's age, height and weight. Subjects who experience a DLT are eligible to receive subsequent cycles of ^{90}Y -DOTA-tyr³-Octreotide at a reduced dose if the DLT has returned to baseline value within 9 weeks of the intolerated ^{90}Y -DOTA-tyr³-Octreotide dose. The subject's subsequent dose must be reduced to 50% of the intolerated dose.

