1.5 Study design

This is a Phase 2 peptide receptor radionuclide therapy trial of ^{90}Y -DOTATOC in patients with somatostatin receptor positive tumors. The somatostatin receptor targeting of the therapeutic will be checked with ^{68}Ga -DOTATOC PET-CT imaging prior to therapy. Treatment consists of 3 cycles, 6-8 weeks apart. Cycle 1 dose is fixed with Cycles 2 and 3 doses to be determined by dosimetry-based calculation of renal doses from previous cycles not to exceed 23 Gy for the total renal dose.

^{68}Ga -DOTATOC PET imaging and ^{90}Y -DOTATOC peptide receptor radionuclide therapy (PRRT) are readily available in Europe, but neither radiopharmaceutical is approved for use in the United States. We are presently conducting a safety and efficacy trial of ^{68}Ga -DOTATOC PET in adults and children under IND# 114,398, that to date has included over 220 subjects with no serious adverse events. We have conducted a single institution Phase I trial of ^{90}Y -DOTATOC therapy in children and young adults under IND# 61,907 with no serious adverse events¹³, and we have participated in a Phase II trial of ^{90}Y -DOTATOC PRRT in adults, also with no dose limiting toxicities²¹.

The total radiation dose to kidneys with PRRT using ^{90}Y -DOTATOC is currently limited to ≤ 23 Gy for both children and adults. Several reports, including dosimetry performed on children in our Phase I trial, have suggested that this dose limit can safely be raised to as high as 35 Gy to kidneys when performing individualized dosimetry measurements to guide therapeutic dosing of ^{90}Y -DOTATOC^{26,29,30}. We have considerable expertise in the development of theoretical models for dosimetry³¹, as well as experience in performing dosimetry in individual patients^{13,32}. These studies demonstrated a wide variation in renal dose, both between patients and between cycles in any given individual. In this Phase II therapeutic trial, we therefore propose to perform dosimetry for each patient during the first and second cycles of therapy. The method for performing the dosimetry will take advantage of a positron decay component of Yttrium-90 that will allow quantification of radiation dose using PET imaging to measure rate of ^{90}Y -DOTATOC into kidneys, coupled with semi-quantitative measurement of bremsstrahlung energy using single photon emission tomography (SPECT) to follow the body clearance of ^{90}Y -DOTATOC over 72 hrs after injection of the therapeutic dose.

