4.0 Objectives

4.1 Primary Objectives

1. Quantify number of CR, PR, MR, SD and progressions in response to dosimetry-guided PRRT utilizing RECIST 1.1 criteria and ⁶⁸Ga-DOTATOC or ⁶⁸Ga-DOTATATE PET to evaluate efficacy of ⁹⁰Y-DOTATOC therapy in children and adults with neuroendocrine and other somatostatin receptor positive tumors.
2. Monitor renal, hematologic, and clinical toxicities associated with dosimetry-guided ⁹⁰Y-DOTATOC PRRT while maximizing total tumor dose and limiting total renal dose of ⁹⁰Y-DOTATOC to ≤ 23 Gy.

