6.3 Measurement of Renal Dose

The following information is required to estimate the dose to the kidneys:

- a) An estimate of the radioactivity accumulated in the kidneys,
- b) The kinetics of the radioactivity, and
- c) The size (mass) of the kidneys.

The renal accumulation of the radiopharmaceutical will be measured with Y-90 DOTATOC time-of-flight PET-CT imaging. A standard of Y-90 will be also imaged. PET images will be reconstructed with an OSEM iterative algorithm that incorporates the time of flight information. The kidney mass will be obtained from CT images.

The methods of kinetic analysis of the renal clearance of Y-90 DOTATOC is modified based on our previous experience. Our analysis of 47 prior administrations demonstrate that the renal clearance of Y-90 DOTATOC follows a biexponential pattern with the majority of the radiation exposure to the kidneys coming from the slow (long) component of clearance after the initial fast elimination. The rate constant of the slow component was gaussian distributed with a standard deviation less than 30% of the mean. This allows us to use a population based rate constant for slow clearance adjusted based on the uptake at 48 hours. The estimated renal radiation dose using this approach shows excellent correlation with the measured radiation dose (See *Appendix 1t: Single Timepoint Dose Estimate for Exponential Clearance*) and allows for a clinically feasible personalized treatment dosimetry with one follow-up visit after 48 hours of treatment administration. The information on renal uptake, renal mass and residence time will be entered into OLINDA software to calculate the radiation dose.

The Phase II studies of ⁹⁰Y-DOTA-tyr³-Octreotide administered to adults suggest that the safe range of ≤ 23 Gy for radiation to kidneys delivered by external beam radiation, is more likely 30-35 Gy when delivered as divided doses of targeted internal radiation⁵⁸. Furthermore, there were no dose limiting renal toxicity events in children or young adults enrolled in the Phase I study. Nevertheless, because of the young age of pediatric subjects described in Aim 1, we limited the total dose to kidneys, including any previous external beam radiation to ≤ 23 Gy. The dose to kidneys measured in Cycles 1 and 2 will be summated for each subject. If this total dose is < 23 Gy, the remaining allowable body activity for that subject will be calculated according to the following formula:

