$$1000 \times (23 \text{ Gy} - \text{summed renal dose (Gy)}) / \text{renal dose per activity (mGy/MBq)}.$$

All subjects will receive a concomitant amino acid infusion as renal protectant¹³. A parenteral amino acid solution which supplies ≥ 27 g each of lysine and arginine in 2 liters of normal saline (≤ 800 mOsm/L) will be administered IV at a max of 8.3 mL/kg/hour (max 450 mL/hr) for 4 hours to begin 30 minutes prior to infusion of ⁹⁰Y-DOTATOC. Initial infusion rate should be 300mL/hr or less; if tolerated for initial 30 min, rate may be increased to max rate. The total minimum volume which shall be infused is 1600 mL. This will constitute an off-label use of these approved amino acid solutions due to the higher than recommended volume infused. Any further information regarding dosing should be obtained from the manufacturer's instructions.

Patients will be pre-medicated with EMEND and Lorazepam, and/or another anti-emetic, 30 minutes prior to the Amino Acid infusion.

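### The 23 Gy kidney limit is a point projection with no stated margin, so some subjects not held by the 420 mCi cap would pass it, and the plan does not report how many

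*Combined protocol and SAP*

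**What the plan says.** Primary Objective 2 (Section 4.1) is to monitor toxicity "while maximizing total tumor dose and limiting total renal dose of" the drug to 23 Gy or less, and hypothesis 2 uses the same limit.

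Section 10.1 gives the planning rule. "Dosimetry will be acquired following treatments 1 & 2". Then "The kidney dose/mCi will be calculated and the total target dose that will limit renal dose to" 23 Gy, and "The target dose minus 120 mCi will then be divided into two equal doses for Cycles 2 and 3", with adjustment on dosimetry. Cycle 2 is at most 150 mCi, Cycle 3 is no higher than Cycle 2, and the total is at most 420 mCi. There is a 25-50% decrease if the probable three-cycle total is above 23 Gy, and a 10-20% increase if it is well below.

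Section 6.3 covers the last step: "The dose to kidneys measured in Cycles 1 and 2 will be summated for each subject". If the sum is below 23 Gy, "the remaining allowable body activity for that subject will be calculated according to the following formula", namely 1000 × (23 Gy − summed dose) / (dose per activity).

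Section 1.5 says of the group's earlier dosimetry: "These studies demonstrated a wide variation in renal dose, both between patients and between cycles in any given individual". Section 8.1 stops treatment once cumulative renal dose exceeds 23 Gy. Section 12.2 tabulates adverse events and does not mention delivered renal dose.

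**The concern.** The rule aims at the limit itself. It treats the dose per activity seen in earlier cycles as the value that will apply in the next one, although the protocol's own background says renal dose changes widely from cycle to cycle. If the kidney takes up more per mCi in the next cycle than was projected, the delivered total passes 23 Gy. This would happen even with exact measurement, because it comes from projecting to the limit and not from the single-time-point method.

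None of the safeguards is built to catch it. The 8.1 stop responds after the event and has nothing left to stop after Cycle 3. The percentage decrease depends on the same point projection.

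What is at stake is the renal safety conclusion. It would be stated for an exposure of 23 Gy or less when an unknown share of subjects received more, and the analysis section would not show that share.

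**Working it through.** The plan gives no probability of exceeding 23 Gy, so there is no figure to reproduce.

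**Inputs from the protocol.** Adult Cycle 1 activity is 120 mCi. The caps are consistent: 120 + 150 = 270 and 270 + 150 = 420 mCi, as in the schema. The 420 mCi cap stops binding above 23/420 = 0.0548 Gy/mCi, which is 54.8/37 = 1.48 mGy/MBq.

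**Inputs not in the protocol, so assumed.**
- Between-cycle CV of kidney dose per mCi: 10-30%.
- Mean kidney dose: 0.06-0.08 Gy/mCi, so that 23 Gy is reached at 383 down to 288 mCi.
- Rate used to plan Cycle 3: either the Cycle 2 rate or the pooled Cycle 1-2 rate.

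**One subject by hand.** Take 0.07 Gy/mCi in Cycles 1 and 2.
- Cycle 1 dose: 120 × 0.07 = 8.40 Gy.
- Target: 23/0.07 = 328.6 mCi, so Cycles 2 and 3 are (328.6 − 120)/2 = 104.3 mCi each.
- Cycle 2 dose: 104.3 × 0.07 = 7.30 Gy. The sum is 15.70 Gy and the remainder 7.30 Gy.
- The formula gives 7.30/0.07 = 104.3 mCi for Cycle 3. The projection is exactly 23 Gy, so the decrease is not triggered.
- If the Cycle 3 rate is 20% higher, its dose is 7.30 × 1.20 = 8.76 Gy and the total is 24.46 Gy, which is 1.46 Gy over.

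**Rough check.** When Cycle 3 activity is set by the renal remainder, the total passes 23 Gy about half the time. The rule that Cycle 3 may not exceed Cycle 2 binds in roughly half of subjects. This gives about 0.5 × 0.5 = 25%.

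**Simulation.** There were 400,000 subjects per setting, with cycle rates g1 to g3 lognormal around the subject's mean and no measurement error. D1 and D2 are the Cycle 1 and 2 doses.
- A1 = 120
- A2 = min(150, (23/g1 − 120)/2)
- A3 = min(A2, (23 − D1 − D2)/planning rate)
- With the decrease, if repeating A2 projects above 23 Gy, A3 is also at most 75% or 50% of A2.

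| Rule (0.06-0.08 Gy/mCi, CV 10-30%) | Share above 23 Gy |
|---|---|
| No percentage decrease | 19-35% |
| 25% decrease | 13-32% |
| 50% decrease | 9-24% |

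The lower end of each range comes from the Cycle 2 rate and the upper end from the pooled rate. The mean excess among those above the limit is about 0.6-2 Gy. Without the decrease, 0.3-11% of subjects pass 25.3 Gy (10% over the limit). At 0.05 Gy/mCi, where the 420 mCi cap binds on average, about 1-10% exceed.

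**Wider assumptions.** With subject means uniform over 0.056-0.15 Gy/mCi, CV 5-40%, and 0 or 10% measurement error, the range among uncapped subjects is about 9-41%. With no re-planning after Cycle 2 it is about 50%.

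**Two rules that give different activities.** In the same subject, let the Cycle 2 rate be 0.077 Gy/mCi.
- Cycle 2 dose: 104.3 × 0.077 = 8.03 Gy. The sum is 16.43 Gy and the remainder 6.57 Gy.
- Section 6.3 at the Cycle 2 rate gives 6.57/0.077 = 85.3 mCi.
- The 25-50% step in 10.1, applied to 104.3 mCi, gives 78.2 down to 52.1 mCi.

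The protocol does not say which governs.

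**The case against.** The strongest reply is that the protocol already answers between-cycle variation: Section 1.5 gives it as the reason for measuring in both Cycles 1 and 2. Section 10.1 adds re-planning, the limit of Cycle 3 to Cycle 2, the percentage decrease and the activity caps. It also speaks of a target and a probable total, which is the language of projection. The objective and hypothesis state an aim and do not promise a value for every subject. Sections 1.5 and 6.3 present 23 Gy as cautious against a suggested 30-35 Gy, and renal toxicity is monitored directly.

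Much of this stands. The safeguards lower the rate and are in the simulation, and most modelled excesses are modest. Section 1.5 also speaks of variation in renal dose, not in dose per mCi, and does not say whether activity differed between those cycles. But the safeguards do not remove the exceedance, and the protocol keeps 23 Gy as its limit whatever it says about higher values.

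A reader might infer that a fifth to a third of uncapped subjects would exceed the limit. The documents do not support that as a finding: it rests on assumed variation and leaves out the percentage decrease, which takes the lower end to about 9%. Nor do they support saying that nothing is ever held back, since the 50% step often lands well below the limit, or that a sizeable part of the whole trial would exceed. The share of subjects above 0.055 Gy/mCi is not given.

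**Conclusion.** The concern holds as a mismatch between the stated limit and the rule meant to deliver it. Sections 10.1 and 6.3 project to 23 Gy from earlier-cycle rates with no stated margin, and Section 1.5 gives reason to expect those rates to move. Some subjects not held by the 420 mCi cap would pass the limit.

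How many cannot be derived from the documents, which give no between-cycle CV, no distribution of Gy/mCi and no statement of which cycle's rate plans Cycle 3. The 9-32% (with the decrease) and 19-35% (without it) are conditional on the assumptions above. They apply to adults starting at 120 mCi. Children, who start at 50 mCi/m², were not modelled.

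This is a defect in how exposure is stated and reported. It does not show that the regimen is unsafe.

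**What to change.** - Reconcile Sections 10.1 and 6.3, hypothesis 2 and Primary Objective 2 with Section 1.5 by stating that 23 Gy is a projected total.
- In Section 12.2, add planned versus delivered renal dose per subject, and the proportion of subjects above 23 Gy with a confidence interval.
- Estimate between-cycle variation in kidney dose per mCi from the existing dosimetry (47 administrations, Section 6.3), using subjects with repeat cycles. Their number is not stated, so the precision is unknown. Prediction intervals for individual projections are optional.
- Reconcile Section 10.1 and the schema, which place dosimetry after Cycles 1 and 2, with the Section 7.0 calendar, which also marks Cycle 3 Day 2. Delivered three-cycle totals cannot be reported without Cycle 3 dosimetry.
- Reconcile the fixed-percentage steps in 10.1 with the 6.3 formula, and state which cycle's rate plans Cycle 3.

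The cost is protocol and SAP wording plus one variance estimate; if Cycle 3 dosimetry is not already intended, measuring it would add imaging. The downside for the sponsor is that the limit is described as projected, with an exceedance rate reported beside it. Whether the dosing rule itself should change is for the sponsor's clinicians and physicists.
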